### 5. OVERALL STUDY DESIGN

This is a single-center, open-label study to evaluate the efficacy and tolerability of a Healing Ointment when used on infants with mild-to-moderate diaper rash.

Protocol GLI.04.US.SL.023

CONFIDENTIAL

Subjects and their parent/legal guardians will report to the site at baseline (day 0) visit, will be given an informed consent form, HIPAA form, photography release form, and medical history form to complete.

Subjects will be screened on the basis of the selection criteria for study qualification. Efficacy assessment (skin health, skin smoothness, skin texture), and tolerability assessment (erythema, dryness, scaling, peeling, edema) will be performed, and baseline photographs will be taken.

Subjects' parent/legal guardians will be instructed to apply the provided Healing Ointment to the groin and buttocks area at every diaper change.

Subjects' parent/legal guardians will complete Day 1 questionnaire at home. Subjects and their parent/legal guardians to return to the site at day 7 ( $\pm 3$  days) and day 21 ( $\pm 3$  days) for follow-ups.

For each follow-up visit, Investigator will perform assessments and photography. Subjects' parent/legal guardians will perform self-assessment questionnaire.

A subject and their parent/legal guardian will be involved in the study for 3 weeks. The study visits are illustrated in **Error! Reference source not found.**

Protocol GLI.04.US.SL.023

CONFIDENTIAL

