## 1. SYNOPSIS

Clinical Study Title:	An open-label study to assess efficacy and safety of a Healing Ointment when used on infants with mild-to-moderate diaper rash
Clinical Trial Number:	GLI.04.US.SL.027
Indication:	Dermatitis
Study population:	Infants at 2- <del>24</del> 35 months of age
Country(ies) Involved and Planned Number of Study Centers:	USA Site: Young Skin [name]
Number of Subjects:	30 subjects to complete
Clinical Study Design:	
This is a single-center, open-label study.
 
Subjects and their parent/legal guardians will report to the site at baseline (day 0) visit, will be given an informed consent form, HIPAA form, photography release form, and medical history form to complete.
 
Subjects will be screened on the basis of the selection criteria for study qualification. Efficacy assessment (skin health, skin smoothness, skin texture), tolerability assessment (dryness, peeling, edema), and self-assessment questionnaire will be performed.
 
Subjects' parent/legal guardians will be instructed to apply the provided Healing Ointment to the buttocks and groin area (if applicable) at every diaper change.
 
Subjects and their parent/legal guardians to return to the site at day 7 (<math>\pm</math> 3 days) and day 21 (<math>\pm</math> 3 days) for follow-ups.
 
For each follow-up visit, investigator will perform objective assessments, tolerability assessments, and photography, if consented. Subjects' parent/legal guardians will perform self-assessment questionnaire.
 
A subject and their parent/legal guardian will be involved in the study for 3 weeks.

Primary Effectiveness Objective and Endpoint:	To evaluate efficacy of a Healing Ointment in skin texture and smoothness in infants 2 to <del>24</del> 35 months old with mild to moderate diaper dermatitis

Secondary Effectiveness Objective(s) and Endpoint(s):	To evaluate subject satisfaction using a Self-Assessment Questionnaire.
Safety Objective and Endpoint	To evaluate safety and adverse events (AEs) throughout the study.
Clinical Study Duration:	The planned clinical study duration (from FSFV to LSLV) is approximately 9 weeks. The planned duration of recruitment is approximately 6 weeks.
Duration of Subject Participation:	Clinical study participation for each subject is 3 weeks

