Investigational Products:	Cetaphil Healing Ointment Fla#1748 (ref.:B50H48)
Treatment Area / Treatment Regimen / Mode of Administration	Healing Ointment will be applied topically to the rash area with every diaper change

Effectiveness Assessments:	
Clinical Grading
 

• Efficacy assessment of skin health, skin smoothness, skin texture compared to baseline

 
Self-Assessment Questionnaire
 

• Parent/legal guardian assessment

Safety Assessments:	
Tolerability assessment of dryness, peeling, edema
 
Safety/tolerability assessment at each visit
 
Adverse Event reporting: AEs will be obtained from signs and symptoms reported by the subject or detected during each examination.

Statistical Methods:	
In general effectiveness, safety and baseline characteristics variables will be presented using descriptive statistics within each treatment group and in combination, and graphs as appropriate. Continuous endpoints will be summarized using descriptive statistics, e.g., mean, median, standard deviation, minimum and maximum values. Categorical endpoints will be presented in frequency tables with number and percentage of observations for each level.

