### 6.4 Exclusion Criteria

1. Subject diagnosed with severe diaper rash
2. History of allergy or hypersensitivity to any ingredient of the test product
3. Presence of any disease or lesions near or on the area to be treated, e.g.,
  - a. Inflammation, active, or chronic infection in or near the treatment area
  - b. Psoriasis, eczema, rosacea, atopic dermatitis, herpes zoster/herpes simplex, and acanthosis
  - c. Scars or deformities

Protocol GLI.04.US.SL.023

CONFIDENTIAL

4. History of coexisting bacterial infections or medical conditions with uncontrolled gastrointestinal diseases and/or bowel movements
5. History of severe elastosis and/or excessive sun exposure that, in the opinion of the Investigator, could have affected the outcome of the study
6. Planning on having surgeries and/or invasive medical procedures during the course of the study
7. Treatment with chemotherapy, immunosuppressive agents, inhaled corticosteroids, immunomodulatory therapy (e.g., monoclonal antibodies or antiviral treatment for human immunodeficiency virus or hepatitis C)
8. Current use of topical corticosteroids, topical prescription, or oral antibiotics in the treatment area, or use within last 2 weeks
9. Current use of over-the counter topical medications for diaper rash
10. History of cancer or previous radiation near or on the treatment area
11. Human immunodeficiency virus positive or active hepatitis
12. Presence of dermal markings on or near the treatment area that, in the opinion of the Investigator, will interfere with the clinical assessments
13. Any medical condition that, in the opinion of the Investigator, would make the subject unsuitable for inclusion (e.g., a chronic or relapsing disease that may interfere with the outcome of the study)
14. Other condition preventing the subject from entering the study in the Investigator's opinion, (e.g., subjects failing baseline assessments, subjects not likely to avoid other cosmetic treatments in the treatment area, subjects anticipated to be unavailable or incapable of understanding the study assessments or having unrealistic expectations of the treatment result).
15. Study site personnel, close relatives of the study site personnel (e.g., parent/legal guardians, children, siblings, or spouse), or employees and close relatives of employees at the Sponsor company.
16. Participation in any interventional clinical study within 30 days of screening

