**Table 3. Grading Scale for Diaper Dermatitis**

Parameters	Normal	Slight	Mild	Moderate	Severe
	0	1	2	3	4
Diaper dermatitis	No clinical sign	Faint to definite pinkness over small area, may be a single raised bump (papule), may be slight dryness	Faint to definite pinkness over small area, definite redness over a very small area, scattered raised bumps (papule),	Faint to definite pinkness in a larger area, definite redness over a small area, very intense redness in a very small	Definite redness in a larger area, very intense redness in a very small area, single to several areas of raised bumps (papules), presence of

			moderate dryness	area, scattered raised bumps (papules), moderate dryness	erosions, may have slight peeling, may have swelling (edema), may have scaling
--	--	--	------------------	--	--

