### 11.3 Tolerability Assessment

Tolerability assessments will be performed by Investigator at each visit prior to treatments with study product and at every follow-up visit. Investigator will grade the degree of irritation parameters that they observe in subject based on a 4-point analog scale, described in [Table 4](#) (with half-point scores used as necessary to better describe the clinical condition).

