**Table 4. Tolerability Assessment Scale**

Parameters	Score 0	Score 1	Score 2	Score 3
Dryness	None	Mild	Moderate	Severe
Peeling	None	Mild	Moderate	Severe
Edema	None	Mild	Moderate	Severe

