### 12.4 Statistical Analysis Plan

Mean of the change from Baseline will be estimated at applicable post-Baseline timepoint. The null hypothesis, that the mean change from Baseline is zero, will be tested using methods described in [Table 5. Statistical Analysis Plan](#).

The following will be calculated and reported for each parameter at applicable post-Baseline timepoint(s):

$$\text{Percent mean change from baseline} = \frac{(\text{visit mean score} - \text{baseline mean score})}{\text{baseline mean score}} \times 100$$

$$\text{Percent of subjects improved/worsened} = \frac{(\text{number of subjects improved/worsened from baseline})}{\text{total number of subjects}} \times 100$$

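### Section 5 lists erythema among the tolerability signs but Tables 4 and 5 neither score nor analyse it there, and the planned summaries of peeling and edema are weak if baseline scores are near zero

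*Combined protocol and SAP*

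**What the plan says.** The list of tolerability signs differs between sections.

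- Section 5 (Overall Study Design): "tolerability assessment (erythema, dryness, scaling, peeling, edema) will be performed".
- Synopsis, study design: "tolerability assessment (dryness, peeling, edema" and nothing further. Synopsis, safety assessments: "Tolerability assessment of dryness, peeling, edema".
- Section 11.3, Table 4 ("Tolerability Assessment Scale"): rows for dryness, peeling and edema only, each scored 0 to 3, "with half-point scores used as necessary to better describe the clinical condition".
- Section 12.4, Table 5: the same three signs, tested by paired t-test, or by Wilcoxon signed-rank test if normality fails. Either a fall in score or the absence of a significant rise is taken to show tolerability.

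Three other places bear on the point. Table 3, the 0-4 diaper dermatitis scale, brings in peeling, edema and scaling only in its Severe column ("may have slight peeling, may have swelling (edema), may have scaling"), and exclusion criterion 1 in Section 6.4 is "Subject diagnosed with severe diaper rash". Section 12.4 requires "Percent mean change from baseline" for every parameter, with the baseline mean as divisor and no rule for a baseline mean of zero. Section 4.2 states the tolerability hypothesis as no statistically significant increase in the tolerability scores at any time point.

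**The concern.** There are two linked problems.

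First, the sections cannot all be followed. Erythema comes first in the Section 3 list of presenting signs and first in the Section 5 tolerability list, yet it is absent from the tolerability scale and its analysis. The tolerability claim in Section 4.2 rests on the scored tolerability signs, so new redness caused by the product could not count against it there.

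Second, two of the three signs that are scored may start at or close to zero in a population without severe rash. A ratio to the baseline mean then has little meaning. In addition, a rule that equates a non-significant increase with good tolerability can pass a visible number of new cases in a study of about 30 infants. What is at stake is whether the report can support its safety conclusion.

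**Working it through.** The plan gives no power calculation, expected baseline score or standard deviation, so there is no figure of its own to reproduce.

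**Step 1: the lists side by side**

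| Sign | Section 5 | Synopsis | Table 4 | Table 5, tolerability | Grades in Table 3 |
|---|---|---|---|---|---|
| Erythema | yes | no | no | no | pinkness 1-3, definite redness 2-4 |
| Dryness | yes | yes | yes | yes | 1-3 |
| Scaling | yes | no | no | no | 4 only |
| Peeling | yes | yes | yes | yes | 4 only |
| Edema | yes | yes | yes | yes | 4 only |

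Two of the five signs in Section 5 have no tolerability scale and no tolerability analysis. Of those two, only erythema is described in Table 3 at the grades that can be enrolled.

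**Step 2: percent mean change at low baselines**

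Inputs: n = 30 (Section 6.1, the maximum number of completers); smallest non-zero score 0.5 (Section 11.3); formula from Section 12.4. The baseline means are assumptions, because the documents give none.

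If one infant worsens by one point, the visit mean rises by 1/30 = 0.0333, so percent mean change = 100 × 0.0333 / baseline mean.

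| Assumed baseline | Baseline mean | Percent mean change |
|---|---|---|
| all at 0 | 0 | undefined |
| one infant at 0.5 | 0.017 | +200% |
| one infant at 1 | 0.033 | +100% |
| three infants at 1 | 0.10 | +33% |
| fifteen infants at 1 | 0.50 | +6.7% |
| all at 1 | 1.00 | +3.3% |

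The same clinical event, one infant one point worse, is reported as anything from +3.3% to +200%, or not at all.

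**Step 3: what the decision rule would pass**

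Assume that all 30 infants score 0 at baseline, k of them score 1 at the visit and the rest stay at 0. The significance level is 5%, two-sided (Section 12.1).

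- Paired t-test: t = √[k(n − 1)/(n − k)] on 29 df. For k = 4, t = √(4 × 29/26) = 2.11.
- Exact signed-rank test with zeros dropped: all k differences are positive and equal, so p = 2 × (1/2)^k.
- Signed-rank by normal approximation without continuity correction: z = √k.

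| New cases k | Percent of 30 | t-test p | Exact signed-rank p | Approximate signed-rank p |
|---|---|---|---|---|
| 3 | 10.0% | 0.083 | 0.25 | 0.083 |
| 4 | 13.3% | 0.043 | 0.125 | 0.046 |
| 5 | 16.7% | 0.023 | 0.0625 | 0.025 |
| 6 | 20.0% | 0.012 | 0.031 | 0.014 |

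Differences that are nearly all zero will fail any normality check, so the Wilcoxon branch would apply. Its exact form first falls below 0.05 at k = 6. Five new cases in 30 (17%, exact 95% CI 5.6% to 34.7%) would therefore count as no significant increase. The t-test and the uncorrected approximation would already flag four. The plan does not say which form of the signed-rank test will be used.

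**The case against.** A reader might infer from Tables 4 and 5 that redness is not graded at all. The documents do not support that. The investigator grades redness at every visit within the diaper dermatitis score, and Table 5 tests that score. The diary in Section 11.2 asks for any symptom in the application area, and Section 13 makes clinically relevant worsening of a protocol parameter an adverse event. What is missing is narrower: a separate erythema score and a tolerability analysis of it. That gap stands, because the composite mixes redness with papules and dryness, so redness can worsen while the grade holds or falls.

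It is also fair to say that Section 5 is the outlier: two entries in the synopsis and both tables agree with each other. The documents do not show which list was intended, and deleting two words from Section 5 would remove the contradiction. It would not give the tolerability claim a measure of redness.

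A reader might also take peeling and edema to be certain zeros at baseline, and so uninformative. Neither follows. Table 3 is not formally tied to eligibility, it words these signs as possible rather than required, Section 3 lists them without a grade, and Table 4 allows mild and half-point scores. A sign that starts at zero also has its full range in which to rise, which is what a tolerability measure is for.

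Finally, Section 12.4 already plans the percent of infants improved or worsened for each parameter, and percent mean change is only descriptive: the Table 5 conclusion rests on the test. This shortens the list of changes but does not remove the unstable ratio, or the reading of a non-significant result as evidence of tolerability.

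**Conclusion.** The point holds in a limited form. The contradiction between Section 5 and the synopsis, Table 4 and Table 5 is plain from the text, and its practical consequence is that redness has no tolerability score or tolerability analysis of its own.

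The second part is conditional. If baseline means for peeling or edema are at or near zero, which is likely from Table 3 and exclusion criterion 1 but not established, percent mean change is undefined or is driven by single infants. Under all-zero baselines, one-point changes, n = 30 and an exact signed-rank test, new signs in up to 5 of 30 infants would be read as tolerated. With the t-test or the uncorrected approximation, the largest number passed is 3 of 30.

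The documents do not support a case for restoring all five signs: scaling is confined to the Severe grade in Table 3, just as peeling and edema are, and would bring the same low-baseline problem. This should be corrected because it affects the safety conclusion; it does not undermine the efficacy analysis.

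**What to change.** 1. Make Section 5, the synopsis, Table 4 and Table 5 agree. The preferred route is to add erythema as a separate 0-3 row in Table 4, in the tolerability row of Table 5 and in the synopsis. If that is not wanted, state in Sections 5 and 11 that redness is assessed only through the Table 3 grade, the diary and adverse event reports, and limit the Section 4.2 tolerability claim accordingly.
2. Scaling need not be added; it can be deleted from Section 5.
3. In Section 12.4, for any tolerability sign with a baseline mean at or near zero, drop percent mean change. Fix the cut-off for near zero before the data are seen. Report the number and percent of infants with new onset or worsening, with an exact 95% CI, beside the planned test.
4. State whether the signed-rank test is exact or approximate and how zero differences are handled.

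The cost is one extra CRF row at an examination that is already done, plus wording changes in the protocol and analysis plan. No extra visit or infant is needed.

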**Figure 1. Study Flow Chart**

## 6. SELECTION AND DISPOSITION OF STUDY POPULATION

### 6.1 Number of Subjects

An appropriate number of subjects meeting inclusion/exclusion criteria listed below will be enrolled on the study to achieve maximum 30 subjects who complete the study as planned.

### 6.2 Study Population Characteristics

- Healthy infant males and females with diaper rash

### 6.3 Inclusion Criteria

1. Subjects of 2-~~24~~35 months of age
2. Females and/or males
3. Subjects of any race and ethnicities
4. Subjects diagnosed with mild-to-moderate diaper rash
5. Subjects of any Fitzpatrick skin types I-VI
6. Subjects with healthy immune systems
7. Willing to be photographed at each visit (optional)
8. Willing to abstain from use of any other topical diaper rash treatments (ointments, moisturizers, emollients, creams, and wipes) other than the assigned test product and skincare products that have been routinely used on the diaper area during the duration of the study
9. Willing to continue using regular brands of face/body cleanser and not to begin use of any new skincare products other than the test product for the duration of the study
10. Parent/legal guardian/legal guardians must be at least 18 years old and are willing and able to present proof of legal guardianship
11. Parent/legal guardian/legal guardian with ability to read, understand and give consent for participation in the study
12. Parent/legal guardians/legal guardians willing to sign a photography release form
13. Parent/legal guardian/guardian must agree to adhere to the procedures and requirements of the study and to report to the site on the day(s) and at the time(s) scheduled for the assessments

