Inclusion criteria:	
The subjects must meet all the following criteria to be eligible for the study:
 
 
1. Infant subjects aged 2 months to 24-35 months
 
2. Females and males
 
3. All Fitzpatrick skin types I-VI
 
4. All races and ethnicities
 
5. Subject diagnosed with mild-to-moderate diaper rash
 
6. Subject with healthy immune systems
 
7. Willing to be photographed at each visit (optional)
 
8. Willing to abstain from use of any other topical diaper rash treatments (ointments, moisturizers, emollients, creams, and wipes) other than the assigned test product and skincare products that have been routinely used on the diaper area during the duration of the study
 
9. Willing to continue using regular brands of face/body cleanser and not to begin use of any new skincare products other than the test product for the duration of the study
 
10. Parent/legal guardian/legal guardians must be at least 18 years old and are willing and able to present proof of legal guardianship
 
11. Parent/legal guardian/legal guardian with ability to read, understand and give consent for participation in the study
 
12. Parent/legal guardians/legal guardians willing to sign a photography release form
 
13. Parent/legal guardian/guardian must agree to adhere to the procedures and requirements of the study and to report to the site on the day(s) and at the time(s) scheduled for the assessments
 

Exclusion criteria:	
The presence of any of the following exclusion criteria excluded a subject from enrollment in the study:
 
 
1. Subject diagnosed with severe diaper rash
 

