### 8.3.3. General Study Instructions

- Throughout the study, parents/legal guardians must ensure subjects to avoid extended periods of sun exposure. Extra care should be taken to wear sunscreen and accessories (i.e., hat) and avoid sun exposure from 10 am to 3 pm.
- Do not use any topical diaper rash and/or moisturizing products on the test area (such as sunscreen, lotion, cream, oil, ointment, wipes), other than the assigned study product, for the duration of the study.
- Do not start using any new body care products other than the provided study product.
- Parents/legal guardians must use the same type of diapers for the duration of the study.

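### Inclusion criterion 8, most naturally read, lets routine diaper-area skincare continue, while the parent instructions in 8.3.3 ban moisturizing products there; the two should be aligned

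*Combined protocol and SAP*

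**What the plan says.** **Eligibility.** Item 8 of 6.3 lists the diaper rash treatments a parent must be willing to avoid, among them moisturizers, emollients, creams and wipes. It then makes an exception for anything "other than the assigned test product and skincare products that have been routinely used on the diaper area during the duration of the study". The Synopsis repeats this, again excepting "skincare products that have been routinely used on the diaper area during the duration of the study", so the phrase is not a slip in one place.

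**Prohibited therapies.** Section 6.5.2 adds nothing of its own and refers back to the inclusion and exclusion criteria.

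**Parent instructions.** Section 8.3.3 tells parents: "Do not use any topical diaper rash and/or moisturizing products on the test area (such as sunscreen, lotion, cream, oil, ointment, wipes". The only exception there is the assigned study product, and the ban runs for the whole study.

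**Related text.**
- Inclusion 9: parents are "not to begin use of any new skincare products other than the test product for the duration of the study".
- Section 8.3.3, third bullet: "Do not start using any new body care products other than the provided study product".
- Inclusion 13: the parent "must agree to adhere to the procedures and requirements of the study".
- Exclusion 9: "Current use of over-the counter topical medications for diaper rash".
- Exclusion 14 gives, as one example left to the investigator's opinion, "subjects not likely to avoid other cosmetic treatments in the treatment area".
- Section 8.3.2: diaper rash treatment products must be stopped and replaced by the study product.

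**The concern.** The two rules cover the same skin and the same three weeks but permit different things. The products in question are not incidental. The primary objective in the Synopsis is skin texture and smoothness, and Table 2 grades roughness and coarseness, which a moisturizer may well affect. Section 3 itself describes emollients as improving barrier function and as recommended at each diaper change.

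The study has one arm, and 12.4 tests mean change from baseline. Nothing in the design can separate the ointment's contribution from that of another leave-on product. The conflict also leaves open what is being tested: the ointment added to the usual moisturizer, or the ointment in its place. If sites or parents resolve it differently from infant to infant, the mean change mixes the two.

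**Working it through.** The plan states no figure on this point, so the check compares the texts.

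**1. Status of each product type under the two rules**

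| Product routinely used on the diaper area | Eligibility criteria and 6.5.2 | Section 8.3.3 |
|---|---|---|
| Over-the-counter diaper rash medication | Current users are out (exclusion 9) | Banned |
| Usual non-moisturizing cleanser | Allowed (inclusion 9 expects regular cleansers to continue) | Not named; not a diaper rash or moisturizing product |
| Non-medicated lotion, cream or oil | Exempt under item 8, natural reading | Banned |
| Wipes | On item 8's list to avoid, but may return through the routine-use exemption | Named in the ban |

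The first two rows agree. The conflict is confined to routine leave-on moisturizing products, with wipes unclear.

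**2. Does other text settle it?**
- Exclusion 9 and 8.3.2 concern diaper rash medications or treatments, so an ordinary lotion can pass both.
- Inclusion 13 is a general promise to follow the study's requirements. It favors 8.3.3 but does not delete the exemption.
- Exclusion 14 offers an example for the investigator's judgment, not a rule.
- Inclusion 9 and the third bullet of 8.3.3 forbid only new products, which fits continued use of old ones.
- No section says which rule prevails.

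**3. Would co-use be visible afterwards?** Section 6.5 requires treatments and therapies to be recorded but does not say whether routine skincare counts. The diary in 8.3.1 is specified for time, diaper changes and applications of the study product. Co-use may therefore go unrecorded.

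**4. Size.** If a share *p* of infants continue a routine product, and it shifts their mean change by δ grade points, the overall mean change shifts by *p* × δ. The documents give neither *p* nor δ, and not the sign of δ. No number follows.

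**The case against.** **Item 8 can be read another way.** The sentence is poorly built and could be taken to mean that parents must abstain from diaper rash treatments and also from routine skincare. That would agree with 8.3.3. It is a strained reading: the words introducing the exception govern both items that follow. It would also sweep in a routine cleanser used on the diaper area, which sits badly with inclusion 9. A criterion open to opposite readings would need rewording in any case.

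**The parent-facing rule is clear.** This stands. A parent who follows 8.3.3 satisfies both rules, and nothing shows parents being told of an exemption. A parent who announces that the usual lotion will continue can be kept out under inclusion 13 or exclusion 14. A reader might infer that every routine user is eligible and then automatically noncompliant. The documents do not support that. The exposed case is a site that relies on item 8 and lets the product continue.

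**Discretion over data exists anyway.** This also stands. Section 7.5 lets the investigator decide whether a noncompliant infant's data are excluded, and the per-protocol definition in 12.2 turns on judged impact. Both apply to any deviation. A reader might infer that this conflict creates that discretion or would change the analysis sets by a calculable amount. Neither follows: the number of infants affected is unknown, and ITT is the primary population.

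**A product in steady use is partly in the baseline score already.** This is a fair limit on the concern. It rules out blaming the whole improvement on the moisturizer, but it does not separate the ointment alone from the ointment plus moisturizer.

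**Conclusion.** The concern holds in a limited form. On its natural reading, item 8 permits a co-intervention on the graded skin that 8.3.3 forbids, and the surrounding criteria narrow the gap without closing it. A site following item 8 could breach the study instructions and confound the primary change from baseline.

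This rests on two assumptions: that item 8 is meant as an exemption, and that some enrolled infants use a non-medicated moisturizing product on the diaper area. The documents do not say how many do. Neither the size nor the direction of any effect can be derived from them. A reader might infer that the efficacy result is biased in the ointment's favor, but the documents do not show that.

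The point merits correction because the remedy is cheap and removes an avoidable confounder. It does not by itself invalidate the planned analysis.

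**What to change.** 1. In item 8 of the Synopsis and of 6.3, delete the exemption for leave-on products and keep only usual cleansers. Item 8 then matches 8.3.3, and 6.5.2 follows because it refers back to the criteria.
2. State in both item 8 and 8.3.3 whether plain cleansing wipes are allowed. Both now list wipes without separating cleansing from moisturizing ones, and the question arises at every diaper change.
3. Add one sentence that an infant who uses a banned product stays in ITT as 12.2 defines it. This is needed because 6.5.2 allows a subject given prohibited therapy to continue for safety evaluation only, which could otherwise be read as removing the infant from the efficacy analysis.

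The cost is a wording amendment approved by the IRB under 15.6 and possibly slightly slower recruitment, since some parents may not want to give up a usual product. No new data or analysis is needed.
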